IRB	Institutional Review Board
IR	Independent Review/Reviewer
ISCL	International Society of Cutaneous Lymphomas
ITT	Intent-to-Treat
iv	intravenous
KKD	Kyowa Kirin Pharmaceutical Development, Inc.
KW-0761	humanized monoclonal antibody against CCR4
LDH	lactate dehydrogenase
Mab	monoclonal antibody
MDC	macrophage derived chemokine
MedDRA	Medical Dictionary for Regulatory Activities
MF	mycosis fungoides
mSWAT	modified Severity Weighted Assessment Tool
NCCN	National Comprehensive Cancer Network
NCI	National Cancer Institute
NCS	not clinically significant
NHL	non-Hodgkin's Lymphoma
NYHA	New York Heart Association
ORR	objective response rate
OS	overall survival
PD	progressive disease
PDF	Portable Document Format
PFS	progression-free survival
PK	pharmacokinetic
PR	partial response
PS	performance status
PT	prothrombin time
PTCL	peripheral T-cell lymphoma
PTT	partial thromboplastin time
QoL	Quality of Life
SAE	serious adverse event
SD	stable disease
SEER	Surveillance Epidemiology and End Results
SGOT	serum glutamic oxaloacetic-transaminase
SGPT	serum glutamic pyruvic-transaminase
SJS	Stevens-Johnson syndrome
SPD	sum of the product of the diameters
SS	Sézary Syndrome
TARC	thymus- and activation-regulated chemokine
TBSA	total body surface area
TEAE	treatment-emergent adverse event
TEN	toxic epidermal necrolysis
TTP	time to progression
ULN	upper limit of normal
US	United States

Abbreviations

USCLC	United States Cutaneous Lymphoma Consortium
WHO	World Health Organization
WOCBP	women of childbearing potential

Definition of Terms

pH	hydrogen ion concentration; negative logarithm of hydrogen ion activity
p.r.n.	as needed
QT interval	in electrocardiography, the time from the beginning of the QRS complex to the end of the T wave.
QTc interval	QT interval corrected for heart rate

1 BACKGROUND AND RATIONALE

1.1 Cutaneous T-Cell Lymphomas

[REDACTED]

[REDACTED]

[REDACTED]

[REDACTED]

[REDACTED]

1.2 Treatment of Cutaneous T-cell Lymphomas

[REDACTED]

[REDACTED]

1.3 Chemokine Receptor 4 and T-Cell Malignancies

[REDACTED]

[REDACTED]

[REDACTED]

[REDACTED]

[REDACTED]

1.4 KW-0761 (mogamulizumab)

[REDACTED]

1.5 Safety and Efficacy of KW-0761

[REDACTED]

[REDACTED]

[REDACTED]

[REDACTED]

1.6 Vorinostat (ZOLINZA®)

[REDACTED]

[REDACTED]

[REDACTED]

[REDACTED]

[REDACTED]

[REDACTED]

[REDACTED]

[REDACTED]

1.7 Rationale

[REDACTED]

[REDACTED]

[REDACTED]

2 OBJECTIVES

2.1 Primary Objectives

The primary objective of this study will be:

- To compare the progression free survival of KW-0761 versus vorinostat for subjects with relapsed or refractory CTCL.

2.2 Secondary Objectives

The secondary objectives will be:

- To compare the overall response rate of KW-0761 versus vorinostat in subjects with relapsed or refractory CTCL;
- To evaluate and compare improvements in QoL measurements, Skindex-29, FACT-G and EQ-5D-3L for subjects receiving KW-0761 versus vorinostat;
- To evaluate and compare improvements in the Pruritus Evaluation (Likert scale & Itchy QoL) for subjects receiving KW-0761 versus vorinostat;
- To estimate the duration of response for both the KW-0761 and vorinostat arms for those subjects with relapsed or refractory CTCL responding to treatment;
- To determine if subjects who relapse on vorinostat can achieve response upon cross over to treatment with KW-0761;
- To further assess the safety of KW-0761;
- To describe the immunogenicity of KW-0761.

2.3 Exploratory Objectives

- To compare the overall survival of KW-0761 versus vorinostat for subjects with relapsed or refractory CTCL;
- To conduct exploratory evaluation of KW-0761 exposure-response relationships.

3 STUDY POPULATION

3.1 Subject Selection

This study will enroll subjects with CTCL who have failed at least one prior course of systemic therapy. This should be adequately documented in the subject's medical record.

3.2 Inclusion Criteria

Subject must meet the following criteria for inclusion in this study:

Signed Written Informed Consent

- 1) Voluntarily signed and dated Institutional Review Board (IRB)/ Ethics Committee approved informed consent form in accordance with regulatory and institutional guidelines. Written informed consent must be obtained prior to performing any study-related procedure;

Age and Sex

- 2) Males and female subjects ≥ 18 years of age at the Pre-treatment Visit, i.e., at the time that written informed consent is obtained, except in Japan where subjects must be ≥ 20 years of age;

Target Population

- 3) Histologically confirmed diagnosis of MF or SS;
 - a. For SS (defined as meeting T4 plus B2 criteria), where the biopsy of erythrodermic skin may only reveal suggestive but not diagnostic histopathologic features, the diagnosis may be based on either a node biopsy or fulfillment of B2 criteria including a clone in the blood that matches that of the skin (Olsen, 2011).
- 4) Stage IB, II-A, II-B, III and IV (Olsen, 2011) (see [Appendix 1](#));
- 5) Subjects who have failed at least one prior course of systemic therapy (e.g., interferon, denileukin diftitox, bexarotene, photopheresis, anti-neoplastic chemotherapy, etc.). Psoralen plus ultraviolet light therapy (PUVA) is not considered to be a systemic therapy;
- 6) Eastern Cooperative Oncology Group (ECOG) performance status score (Oken, 1982) of ≤ 1 (see [Appendix 2](#)).
- 7) The subject has resolution of all clinically significant toxic effects of prior cancer therapy to Grade ≤ 1 by the National Cancer Institute Common Terminology

Criteria for Adverse Events, version 4.0 (NCI-CTCAE, v.4.0) excluding the specifications required in 8, 9 and 10 below.

- 8) Adequate hematological function:
 - a. absolute neutrophil count (ANC) $\geq 1,500$ cells/ μL ($\geq 1,500/\text{mm}^3$);
 - b. platelets $\geq 100,000$ cells/ μL ($\geq 100,000/\text{mm}^3$);
 - c. in subjects with known bone marrow involvement, ANC must be $\geq 1,000$ cells/ μL ($\geq 1,000/\text{mm}^3$) and platelets $\geq 75,000$ cells/ μL ($\geq 75,000/\text{mm}^3$).
- 9) Adequate hepatic function:
 - a. bilirubin ≤ 1.5 times the specific institutional upper limit of normal (ULN), except for subjects with Gilbert's syndrome;
 - b. aspartate transaminase (AST) and alanine transaminase (ALT) each $\leq 2.5 \times \text{ULN}$ or $\leq 5.0 \times \text{ULN}$ in the presence of known hepatic involvement by CTCL.
- 10) Adequate renal function:
 - a. serum creatinine $\leq 1.5 \times \text{ULN}$
or
 - b. calculated creatinine clearance > 50 mL/min using the Cockcroft-Gault formula.
- 11) Subjects previously treated with anti-CD4 antibody or alemtuzumab are eligible provided their CD4+ cell counts are $\geq 200/\text{mm}^3$.
- 12) Subjects with MF and a known history of non-complicated staphylococcus colonization/infection are eligible provided they continue to receive stable doses of prophylactic antibiotics.
- 13) Women of childbearing potential (WOCBP) must have a negative pregnancy test within 7 days of receiving study medication.
- 14) WOCBP must agree to use effective contraception, defined as oral contraceptives, double barrier method (condom plus spermicide or diaphragm plus spermicide) or practice true abstinence from sexual intercourse (periodic abstinence, e.g., calendar, ovulation, symptothermal, post-ovulation methods and withdrawal are not acceptable methods of contraception) during the study and for 3 months after the last dose. WOCBP includes any female who has experienced menarche and who has not undergone successful surgical sterilization or is not postmenopausal (defined as amenorrhea ≥ 12 consecutive months without an alternative medical cause).
- 15) Male subjects and their female partners of child bearing potential must be willing to use an appropriate method of contraception defined as oral contraceptives, double barrier method (condom plus spermicide or diaphragm plus spermicide) or practice true abstinence from sexual intercourse (periodic abstinence, e.g., calendar, ovulation, symptothermal, post-ovulation methods and withdrawal are not acceptable methods of contraception) during the study and for 3 months after the last dose.

NOTE: For subjects continuing to receive study treatment as of protocol Amendment 8, the period of contraceptive use should be extended to 6 months after the last dose of KW-0761.

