- a: If progression is noted at Day 26-28, visit should take place before initiation of new therapy. In cases where the definition of PD or relapse is met but the clinical impression is questionable, subjects may remain on study until the next evaluation (4 weeks later if questionable finding in skin or blood; 8 weeks later in first year and 16 weeks later after Year 1 if questionable finding in lymph nodes or viscera, with at least stable disease in other compartments) to avoid a subject being removed prematurely from the study. For subjects receiving a subsequent treatment course, procedures performed at this time can also be used to satisfy the Day 1 requirements for the subsequent course, provided they are performed within ± 2 days of next KW-0761 administration. For subjects who will not receive subsequent treatment, this visit will be considered the final treatment visit and subjects should undergo testing/procedures specified for End-of-treatment visit (See Table 3).
- b: Complete physical examination including height at Pre-treatment Visit; brief physical examination of pertinent systems at other times. Responses to questions for surveillance of autoimmune type symptoms (See Appendix 4) should be documented at time of physical exam.
- c: For subjects receiving KW-0761, vital signs will be checked and recorded prior to the start of each infusion, at the end of each infusion and 1 hour after the completion of the infusion. For subjects taking vorinostat, vital signs can be taken irrespective of dosing. Weight will be checked with vitals.
- d: Blood can be drawn 1 day prior to visit, if needed, to ensure results are available. In subjects receiving KW-0761, results must be reviewed prior to infusion. The platelet count must be $\geq 100,000 / \text{mm}^3$ and the ANC must be $\geq 1,500/\text{mm}^3$ before a subject can receive study drug.
- e: Serum samples will be collected for subjects treated with KW-0761 pre-dose on days indicated (sample collection will still be needed even if dosing is not performed at a visit), as applicable. On Day 1, an additional sample should be obtained from the arm contralateral to that of study drug administration at the end of infusion (10-15 minutes after completion of the infusion) as well. At selected sites, 4 additional samples will be drawn between 6 and 8 hours, and at 24, 48, and 72 - 96 hours after the first infusion on Day 1.

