3.4 Eligibility for Cross-over to KW-0761

Subjects who are randomized to the vorinostat arm may cross over to KW-0761 upon progression or in the event of intolerable toxicity (see Section 5.3). Crossover may take place following discussion with the Medical Monitor or designee and receipt of approval for cross over from Kyowa Kirin Pharmaceutical Development, Inc. (KKD). However, they must

continue to fulfill inclusion criteria 6 through 15, and will be excluded if they fulfill the exclusion criteria, except for exclusion criteria 1, 12 and 13 (refer to Section 3.3).

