5 TREATMENT PLAN

5.1 Assignment to Study

After a subject signs consent, screening numbers should be assigned by the investigator (or designee) using ClinTrak Interactive Voice/Web Response System (CTIVRS). Once assigned, numbers for any screen failures or non-treated, non-evaluable, or discontinued subjects will not be re-used.

A subject who meets all entry criteria will be randomized in a 1:1 ratio to receive KW-0761 or vorinostat. The randomization to treatment groups will be stratified by disease type (MF or SS) and disease stage (IB/II or III/IV). When a subject is determined to be eligible for randomization the investigator (or designee) will contact CTIVRS to obtain the randomization assignment for the subject. If a subject is randomized in error, or a dosing error occurs, KKD (or designee) should be notified as soon as the error is discovered.

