5.2.1.6 Dose Modifications

No dose modifications of the KW-0761 will be permitted in this study.

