5.4.1 Permitted Treatment

- Hematopoietic growth factors and erythropoiesis-stimulating agents (based on threshold and target hemoglobin levels in the American Society of Hematology (ASH)/American Society of Clinical Oncology (ASCO) guidelines) (Rizzo, 2010) are allowed, if consistent with regional approved prescribing information, after completing Cycle 1.

- Subjects on a stable dose of a low dose systemic corticosteroid (≤ 20 mg prednisone equivalent) for at least 4 weeks prior to the Pre-treatment Visit may continue use. Subjects may receive intra-articular corticosteroid injections, intraocular corticosteroids drops, inhalation or nasal corticosteroids and replacement doses of systemic corticosteroids as needed.
- Subjects on a stable dose of medium or low potency topical corticosteroids for at least 4 weeks prior to the Pre-treatment Visit may continue use at the same dose, although the investigator should attempt to taper the use to the lowest dosage tolerable while on study.
- Prophylactic treatment for the infectious complications of T-cell lymphoma is permitted at the discretion of the investigator.
- For subjects receiving vorinostat, prolongation of prothrombin time (PT) and International Normalized Ratio (INR) have been observed in subject receiving concomitant therapy with coumarin-derivative anticoagulants, carefully monitor PT and INR in these subjects.
- Influenza vaccination consisting of killed virus or viral particles may be administered to subjects on study. Subjects should not receive an influenza vaccine containing live attenuated virus. It should also be understood that because KW-0761, as well as CTCL, can affect the immune system, immunity to influenza may not be achieved despite vaccination.

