8.1.3 Study Drug Administration

Subjects will receive KW-0761 as an iv infusion over at least 1 hour for all infusions. Subjects will be observed closely for 1 hour following each administration of KW-0761 for

any potential AEs in an area with resuscitation equipment. Vital signs will be checked and recorded prior to start of infusion, at the end of the infusion and at 1 hour after completion of infusion.

Hematology results should be reviewed before each subsequent dose. Laboratory assessments may be performed the day prior to dosing to ensure results are available prior to dosing. The platelet count must be $\geq 100,000 / \text{mm}^3$ and the ANC must be $\geq 1,500/\text{mm}^3$ before a subject can receive study drug. If a scheduled dose cannot be given within the allowed window, the dose should be skipped and the subject should resume dosing with the next scheduled dose assuming the platelet count and ANC are within the parameters described above. If a subject misses 2 consecutive doses, contact the Medical Monitor or designee to determine if the subject should be withdrawn from the trial.

Should a hypersensitivity reaction to KW-0761 occur, the subject must be treated according to the best available medical practices. Subjects should be instructed to report any delayed reactions to the investigator immediately. See Section 5.2.1.7 for additional information regarding the treatment of infusion reactions.

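### Criterion 8c admits marrow-involved subjects at neutrophil and platelet counts below the floor at which KW-0761 may be given

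*Protocol*

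**What the plan says.** **Entry.** Criteria 8a and 8b in Protocol section 3.2 set the general floors: ANC 1,500/mm³ and platelets 100,000/mm³. Criterion 8c lowers them: "in subjects with known bone marrow involvement, ANC must be" at least 1,000/mm³, and platelets at least 75,000/mm³. The synopsis repeats this. Section 5.1 then says: "A subject who meets all entry criteria will be randomized in a 1:1 ratio to receive KW-0761 or vorinostat".

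**Dosing.** Section 8.1.3 requires platelets of at least 100,000/mm³ and ANC of at least 1,500/mm³ "before a subject can receive study drug". Table 1 footnote d (first cycle) and Table 2 footnote e (later cycles in year 1) state the same limits, each after this instruction: "In subjects receiving KW-0761, results must be reviewed prior to infusion".

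**When a dose is blocked.** Under section 8.1.3 a dose that cannot be given in its window is skipped, and dosing picks up at the next scheduled dose "assuming the platelet count and ANC are within the parameters described above". After two doses missed in a row, the Medical Monitor is consulted about withdrawal. Section 5.2.1.6 adds: "No dose modifications of the KW-0761 will be permitted in this study". Under section 5.4.1, hematopoietic growth factors "are allowed, if consistent with regional approved prescribing information, after completing Cycle 1".

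**Crossover.** Section 3.4 requires vorinostat subjects moving to KW-0761 to "continue to fulfill inclusion criteria 6 through 15", so 8c applies again. Crossover also needs discussion with the Medical Monitor and sponsor approval.

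**The concern.** The dosing rule matches 8a and 8b but not 8c. Followed to the letter, the protocol can randomize a subject to a drug and then forbid giving it at the counts it accepted for entry. Nothing requires the counts to reach the dosing floor before randomization.

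Such a subject is in the ITT set (Protocol 10.1), and PFS runs from randomization (10.3). Time without the allocated drug therefore counts in the KW-0761 arm. If the subject withdraws, without progression, before any post-baseline tumor assessment, PFS is censored at the last documented visit (SAP 6.11.1.1). The limit falls on one arm: vorinostat follows the US prescribing information, which allows dose omission, reduction or interruption (5.2.2, 5.2.2.5).

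The group is foreseeable. Table 1 footnote l offers marrow examination, as the investigator judges, to subjects with cytopenia or another clinical reason to suspect marrow disease. Known marrow involvement and low counts can thus be expected together.

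**Working it through.** There is no plan figure to reproduce. The check sets the thresholds side by side and follows a subject through the rules.

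| | Entry under 8c (3.2) | KW-0761 dosing (8.1.3; Table 1 d; Table 2 e) | Shortfall | Entry floor ÷ dosing floor |
|---|---|---|---|---|
| ANC (/mm³) | 1,000 | 1,500 | 1,500 − 1,000 = 500 | 1,000 / 1,500 = 66.7% |
| Platelets (/mm³) | 75,000 | 100,000 | 100,000 − 75,000 = 25,000 | 75,000 / 100,000 = 75% |

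1. **Who is in the gap.** A subject with known marrow involvement and ANC from 1,000 to 1,499, or platelets from 75,000 to 99,999, meets 8c and fails the dosing rule. Both dosing limits must be met, so either count alone blocks the dose. Marrow-involved subjects already at 1,500 and 100,000 are unaffected.

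2. **First dose.** The paragraph in 8.1.3 opens by asking for hematology review ahead of every *subsequent* dose, which could be read as sparing the first. Its threshold sentence carries no such limit, and Table 1 footnote d asks for review ahead of infusion without exempting Day 1. The grid of Table 1 was not readable in the text reviewed, so the visits that carry footnote d could not be checked. A bar on Day 1 is probable, not certain.

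3. **Later doses.** Cycle 1 infusions fall on Days 1, 8, 15 and 22 (5.2.1). From Day 8 both readings apply the limit.

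4. **Review of withdrawal.** If Day 1 is barred, Days 1 and 8 are the first two consecutive missed doses, so the Medical Monitor is contacted 8 − 1 = 7 days after treatment was due to start. If Day 1 is given, the pair is Days 8 and 15. Neither path waives the limit.

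5. **Ways out within Cycle 1.** Growth factors are not allowed until the cycle is complete, and a lower dose is not permitted. Only recovery of the counts releases the dose.

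6. **Crossover.** The same two floors meet again, because 3.4 re-applies criterion 8 in full.

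**The case against.** The strongest reply is that an easier entry limit with a stricter dosing hold may be deliberate: admit marrow disease, then wait for the counts. Screening may precede treatment by up to 30 days (section 7), counts can rise, and growth factors are available after Cycle 1, so an ANC gap need not last. Two missed doses bring in the Medical Monitor, and crossover has its own approval step. Time off drug counted from randomization is ordinary intention-to-treat and follows any dose hold, such as one for rash.

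Much of this stands. It limits the consequence and explains why the point is minor. It does not remove the conflict: no passage says that waiting is the intent, no passage requires recovery before randomization, and neither the Medical Monitor contact nor crossover approval lifts the limit. A hold for rash arises after treatment starts, whereas this one can be foreseen at entry.

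A reader might infer more in three ways, none of which the documents support.

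- *These subjects will never be dosed.* Recovery is possible, and the first dose may escape the check.
- *The hazard ratio is biased in a known direction.* That depends on how many subjects are affected, how long they go untreated and whether they withdraw. None of this is given.
- *The crossover mismatch distorts the primary comparison.* A subject who crosses over on progression already has a PFS event.

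**Conclusion.** The inconsistency is real and minor. Following the plan exactly, a marrow-involved subject with ANC 1,000 to 1,499 or platelets 75,000 to 99,999 is eligible for randomization to KW-0761 but barred from it while either count stays there. The bar is certain from Cycle 1 Day 8 and probable on Day 1.

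The size cannot be computed. The documents give no number with known marrow involvement or with counts in the gap, and it is probably very small. Any never-dosed cases would sit within the disposition line in SAP 6.6 for randomized subjects given no study drug, which does not separate them by reason.

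The conclusion assumes that 8c is an exception to 8a and 8b, since otherwise it would have no effect. It also assumes that the dosing limits apply to every KW-0761 subject as written.

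**What to change.** **Preferred.** Delete 8c from section 3.2 and the synopsis. Entry and crossover counts then match the KW-0761 dosing floor, and section 3.4 needs no edit. The cost is a short amendment in two places and slightly narrower eligibility in both arms. Counts that fall after entry stay under the existing skip rule.

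**Alternative, only if clinical safety review accepts dosing at the lower counts.** Keep 8c and add one exception to section 8.1.3, Table 1 footnote d and Table 2 footnote e. The Table 3 hematology footnote, which was not readable in the text reviewed, needs it too if it repeats the limits. Suggested text: *A subject with known bone marrow involvement who qualifies under criterion 8c, at randomization or at crossover, may receive KW-0761 if ANC is ≥ 1,000/mm³ and platelets are ≥ 75,000/mm³.* Naming both time points matters, because a vorinostat subject may enter with normal counts and first rely on 8c at crossover. The cost is a looser dosing limit for a few subjects, edits in three or four places, and safety sign-off.

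Either change helps only subjects not yet randomized or crossed over.

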3.3 Exclusion Criteria

Subjects with any of the following will be excluded from the study:

Medical History and Concurrent Diseases

- 1) Current evidence of large cell transformation (LCT). Subjects with clinical features suggestive of LCT must have a biopsy performed within 4 months prior to Cycle 1 Day 1 to rule out transformed disease. Subjects with a history of LCT but without current aggressive disease and no current evidence of LCT on pathology in skin or lymph nodes would be eligible.
- 2) Diagnosed with a malignancy in the past 2 years. However, subjects with non-melanoma skin cancers, melanoma in situ, localized cancer of the prostate with current prostate-specific antigen of < 0.1 ng/mL, treated thyroid cancer or cervical carcinoma in situ or ductal/lobular carcinoma in situ of the breast with in the past 2 years may enroll as long as there is no current evidence of disease.
- 3) Clinical evidence of central nervous system (CNS) metastasis.
- 4) Psychiatric illness, disability or social situation that would compromise the subject's safety or ability to provide consent, or limit compliance with study requirements.
- 5) Significant uncontrolled intercurrent illness including, but not limited to:
 - a. uncontrolled infection requiring antibiotics;
 - b. clinically significant cardiac disease (class III or IV of the New York Heart Association [NYHA] classification, see [Appendix 3](#));
 - c. unstable angina pectoris;
 - d. angioplasty, stenting, or myocardial infarction within 6 months;
 - e. uncontrolled hypertension (systolic blood pressure (BP) > 160 mm Hg or diastolic BP > 100 mm Hg, found on 2 consecutive measurements separated by a 1-week period) despite 2 anti-hypertensive medications;
 - f. clinically significant cardiac arrhythmia or
 - g. uncontrolled diabetes.
- 6) Known or tests positive for human immunodeficiency virus (HIV), human T-cell lymphotropic virus (HTLV-1), hepatitis B or hepatitis C disease.
- 7) Active herpes simplex or herpes zoster. Subjects on prophylaxis for herpes who started taking medication at least 30 days prior to the Pre-treatment Visit, and have no active signs of active infection, and whose last active infection was more than 6 months ago, may enter the study, and should continue to take the prescribed medication for the duration of the study.
- 8) Experienced allergic reactions to monoclonal antibodies or other therapeutic proteins.
- 9) Known active autoimmune disease will be excluded. (For example, Graves' disease; systemic lupus erythematosus; rheumatoid arthritis; Crohn's disease; psoriasis).
- 10) Is pregnant (confirmed by beta human chorionic gonadotrophin [β -HCG]) or lactating.

Prohibited Therapies and/or Medications

- 11) Prior treatment with KW-0761.
- 12) Prior treatment with vorinostat. Patients who were exposed to vorinostat for a short time, did not progress while on treatment, and did not have intolerable toxicity but were discontinued for another reason (e.g., comorbidity) may be permitted to enter the study after discussion with the Medical Monitor.
- 13) Have had any therapy directed against the subject's underlying cancer or any investigational medications within four weeks of randomization (skin directed treatments, including topicals and radiation within 2 weeks of randomization). However, subjects with rapidly progressive malignant disease may be enrolled prior to this period after discussion with the Medical Monitor.
- 14) Subjects on a stable dose of a low dose systemic corticosteroid (≤ 20 mg prednisone equivalent) for at least 4 weeks prior to the Pre-treatment Visit may continue use although the investigator should attempt to taper the use to the lowest dosage tolerable while on study. Initiation of treatment with systemic corticosteroids or increase in dose while on study is not permitted except to treat an infusion reaction (see Section 5.2.1.7). Subjects may receive intra-articular corticosteroid injections, intraocular corticosteroid drops, inhalation or nasal corticosteroids and replacement doses of systemic corticosteroids as needed.
- 15) Subjects on a stable dose of medium or low potency topical corticosteroids for at least 4 weeks prior to the Pre-treatment Visit may continue use at the same dose, although the investigator should attempt to taper the use to the lowest dosage tolerable while on study. Initiation of treatment with topical corticosteroids while on study is not permitted except to treat an acute rash.
- 16) History of allogeneic transplant.
- 17) Autologous hematopoietic stem cell transplant within 90 days of the Pre-treatment Visit.
- 18) Subjects on any immunomodulatory drug for concomitant or intercurrent conditions other than T-cell lymphoma or who have received any of these agents within 4 weeks of treatment, including but not limited to the following, will be excluded: low dose or oral methotrexate; azathioprine; iv immunoglobulin; low dose or oral cyclophosphamide; cyclosporine; mycophenolate; infliximab; etanercept; leflunomide; adalimumab; lenalidomide; abatacept; rituximab; anakinra; interferon- β ; IL-2 and natalizumab.

